Registry data from 457 recurrent GBM patients who started Optune™ prescribed by the treating physician in the US between October 2011 and November 2013 showed an even higher median overall survival of 9.6 months, with baseline characteristics similar to those of patients treated under the pivotal clinical trial¹⁷. The 2-year survival rate in this population was 30% (compared to 9% in Optune™-treated patients on the clinical trial). Compliance was a clear predictor of survival on Optune™, and patients treated with the device for at least 18 hours per

day had significantly longer survival time. No new safety signals have been detected in this registry dataset and the only common adverse event related to Optune™ was dermatitis. Based on this clinical data in recurrent GBM and a pilot trial in newly diagnosed GBM with Optune™ in combination with temozolomide that demonstrated favorable safety profile and promising efficacy, an international phase III trial in newly diagnosed GBM, evaluating the role of Optune™ in combination with temozolomide maintenance after surgery and chemoradiation versus temozolomide alone was conducted¹⁴. An interim analysis included 210 patients randomized to TTFields plus temozolomide and 105 randomized to temozolomide alone, and was conducted at a median follow-up of 38 months (range, 18-60 months). Median progression-free survival in the intent-to-treat population was 7.1 months (95% CI, 5.9-8.2 months) in the Optune™ plus temozolomide group and 4.0 months (95% CI, 3.3-5.2 months) in the temozolomide alone group (hazard ratio [HR], 0.62 [98.7% CI, 0.43-0.89]; P = .001). Median overall survival in the per-protocol population was 20.5 months (95% CI, 16.7-25.0 months) in the Optune™ plus temozolomide group (n = 196) and 15.6 months (95% CI, 13.3-19.1 months) in the temozolomide alone group (n = 84) (HR, 0.64 [99.4% CI, 0.42-0.98]; P = .004). Quality of life and gross cognitive function were also comparable in the 2 arms¹⁸.

Based on the data submitted to FDA from this newly diagnosed GBM study, FDA approved Optune™ in combination with temozolomide for the treatment of adult patients with newly diagnosed GBM on October 5, 2015. In the US, Optune™ with temozolomide is indicated for the treatment of adult patients with newly diagnosed, supratentorial glioblastoma following maximal debulking surgery and completion of radiation therapy together with concomitant standard of care chemotherapy.

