Two weeks after trimodal therapy, patients will receive a skin exam, scalp assessment and neurologic exam at Day 64 and will also be monitored at 4 weeks (Day 1 of Cycle 1 of adjuvant TMZ) and 8 weeks (Day 1 of Cycle 2 of adjuvant TMZ) after trimodal therapy to assess for post treatment toxicity that may be delayed. After conclusion of the DLT window, the treatment of

patients will be carried out per the standard of care in addition to continued TTFields therapy, as outlined in the clinical trial-related procedures section. The trial will then follow the clinical outcomes including duration of TTF use, completion of 6 cycles of temozolomide, and progression free survival at 6 months, and median overall survival and overall survival at 2 years.

Primary Study Endpoints

- Rate of treatment-related adverse events (TRAЕ)
- Rate of treatment-related severe adverse events (TRSAЕ)
- Rate of Dose-limiting toxicity (DLT)

Given that the primary objective of this study is to determine the safety and tolerability of adding TTField therapy to combined chemoradiation, our primary endpoints are related to safety as follows: Identify the rate of treatment-related adverse events as well as the rate of any severe adverse events during the combined treatment period and up to 8 weeks afterwards. For the same time frame, we will also document and assess the rate of dose-limiting toxicities. Safety of combined adjuvant treatment with TTFields and TMZ chemotherapy outside of the initial radiation is not a primary objective and will not be formally assessed in this study. The above endpoints will be assessed initially in the interim safety analyses involving the safety lead-in cohorts and then also in the main expanded cohort for the final analysis. See statistical methods for further details of the planned analysis. For any skin toxicity grade II or greater, we will also investigate and document, if apparent, whether this was related to the adhesive vs the ceramic disc component of the device.

Secondary Study Endpoints

- PFS6
- Overall survival (median OS and rate of OS at 2 years)
- Objective response by modified RANO criteria
- Median duration of TTFields use and rate of TTF compliance

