- Complete blood count (CBC) with differential and platelet count
- Adverse event assessment
- Concomitant medication review
- Continue TTField therapy

Study procedures, Adjuvant therapy phase and monitoring of delayed toxicities until 8 weeks after completion of trimodal therapy.

This would fall 4 weeks after completion of radiation therapy and marked by initiation of TMZ chemotherapy on a 5 out of 28-day cycle along with continued TTField therapy per the standard of care. MRIs are recommended every 2 months during temozolomide therapy. Day 1 of cycle 1 and cycle 2 are marked by continued treatment per the standard of care along with assessments for delayed TRAEs following trimodal therapy and continued DLT window (4 weeks and 8 weeks after completion of trimodal therapy).

Adjuvant TMZ therapy, Day 1 of Cycle 1 (Study Day 78 ± 5 days) with delayed toxicity monitoring.

- MRI of the brain with and without contrast (transducer arrays will need to be removed/replaced for imaging)
- Vital signs: weight, temperature, pulse, respiration rate, and resting blood pressure.
- Physical examination including neurologic exam, skin and scalp assessment.
- Skin examination by investigator or subinvestigator in Neuro-Oncology (document attribution, grade of toxicity, and if there is apparent correlation with the ceramic disc or adhesive gel on the transducer arrays). If there are concerns of worsening skin toxicity, referral to dermatologist for specialist evaluation (transducer arrays will need to be removed/replaced for exam).
- Adverse event assessment
- Concomitant medication review
- Documentation of disease assessment, clinical response or deterioration, status and extent of measurable disease on imaging
- Objective response assessment
- KPS (performance) assessment
- Complete blood count (CBC) with differential and platelet count
- Blood chemistry assessment, including:
 - Alkaline phosphatase, aspartate aminotransferase/alanine aminotransferase (ALT/AST), total bilirubin, calcium, blood urea nitrogen (BUN), creatinine, total protein, albumin, fasting glucose, potassium, sodium, chloride, bicarbonate
- Initiate Cycle 1, day 1 treatment of adjuvant TMZ on a 5 out of 28-day cycle as detailed under treatment modalities. Dosing will start at 150mg/m²/day for the first cycle and then increased if tolerated to 200mg/m²/day for all subsequent cycles.

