1. Patient training: Patients will be trained in the use of the device by the investigator, a designated health care provider (e.g. nurse, medical assistant, research coordinator) or Device Support Specialist (DSS) trained by Novocure.
2. Treatment initiation: Optune™ will be initiated by the investigator within 7 days of the day 1 clinic visit. All patients will be required to shave their heads to initiate array placement and Optune™. Array placement will be performed based on the Transducer Array Layout map calculated during treatment planning. The investigator or the device specialist will train patients on how to use the map and avoid placing the discs on protruding craniotomy plates, screws, and scars.
3. Treatment duration: Treatment with the device will be continuous with breaks allowed for personal needs (e.g. showering, array exchange). Patients must use the device for at least 18 hours a day on average. Treatment will be continued until tumor progression, death, or unacceptable side effects to patient. Patients must use the device for a minimum of 4 weeks from treatment initiation. A treatment break of 3 days in Optune™ every month is allowed. However, the patient should use the device for at least 18 hours a day on average as stated above.
4. The Optune™ System will be programmed by Novocure to deliver 200kHz TTFields in two sequential, perpendicular field directions at a maximal intensity of 707mA RMS. There will be no adjustments made to the device by investigators or patients/caregivers.
5. Transducer Array replacement: Patients will replace the Transducer Arrays twice to three times per week with the help of a caregiver. The Transducer Arrays will need to be replaced at study visits that require them to be removed to complete a protocol required procedure. At each array replacement the patient's scalp will be re-shaved and skin treated according to the guidelines set out below.

6. Compliance assessment: The device usage will be extracted by a Novocure representative and the data will be reported to the investigator on a monthly basis to assess patient compliance with therapy. Patients who are using the TTField treatment less than 75% of the minimum recommended usage of 18 hours a day on average, as assessed monthly (13 hours a day or less), unless per officially instituted dose reduction, may discontinue therapy at the discretion of the investigator or sponsor.

7. The following skin care guidelines should be closely adhered to:

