In the event of a dose-limiting toxicity, the subject will be discontinued from treatment and followed for toxicity assessment and management and a joint decision will be made by the investigator and sponsor whether to adjust the dose or schedule for other subjects or permanently close the study for safety. In the event that more than 33% of subjects experience a DLT, the study cannot continue unless a modification is made to the level of the particular treatment to which that adverse event is definitely attributable. As preliminary safety stops, the study will include two safety lead-ins receiving TTFields with concurrent chemoradiation. These initial 6 and then 15 subjects will undergo interim analyses after completion of chemoradiation to determine if the expanded cohorts should be permitted enrollment as planned or if a dose reduction in TTFields of 50% of the scheduled use is warranted for safety.

Subjects will continue to receive study treatment until confirmed tumor progression, unacceptable toxicity, or other discontinuation criteria as described; subjects MUST discontinue investigational product (and non-investigational product at the discretion of the investigator) if they meet criteria for removal from study therapy as referenced in that section.

Toxicity related to TTFields treatment: Treatment-related adverse events (TRAEs) and severe treatment-related adverse events (STRAEs) will be assessed in the following ways.

- Patients will be evaluated by a neuro-oncologist or radiation oncologist for potential skin toxicity from TTFields therapy. Routine skin care recommendations will be provided, including use clobetasol cream prior to electrode placement and adjusting array placement to avoid continued site irritation. If there are concerns by investigator, the subject will be referred to a dermatologist for specialized evaluation. Neurological and general physical evaluations as well as laboratory assessments will also be conducted by a neuro-oncologist or radiation oncologist to identify other potential toxicities.
- In addition to clinic visits and interventions, Patients will also be supported by a technician from Novocure for device troubleshooting and compliance checks.
- All other adverse effects, either mild, or serious, will be triaged by a physician in coordination with the primary investigators of the study.

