MRIs in this study will be evaluated centrally by the principal investigator according to RANO criteria and definitions and need to account for possible pseudoprogression from any of the treatments. Therefore, in this trial, if a subject has an MRI scan concerning for progression without substantial neurological symptoms or signs within 6 months of starting TTFields therapy, it is recommended that the subject continue therapy and obtain a follow-up scan approximately 4 weeks apart to confirm progression. If that follow-up scan confirms progression, the patient shall be taken off the study treatments. If that scan is stable when compared to the prior scan, then pseudoprogression will be noted and treatment will continue. If a subject whose scan is concerning for progression also develops substantial neurological decline, or requires increasing steroid dose beyond the daily limit of 8mg dexamethasone for more than 4 weeks, then no confirmatory scan is needed; progression will be noted and that subject shall be discontinued from the study treatments. Similarly, no confirmatory scan is needed if a subject develops MRI changes concerning for progression with or without substantial neurological decline after 6 months of initiating TTFields therapy.

Reporting of Adverse Events

Evaluation of Safety

Analyses will be performed for all patients having received at least one day of TTFields therapy. The study will use the CTCAE v5.0 for reporting of non-hematologic adverse events and modified criteria for hematologic adverse events, see Section 7a (Subject assessments for evaluation of safety and tolerability).

There will not be a formal Study Chair. There will be three DSMC members who will share the responsibility of monitoring study conduct and safety across participating sites.

Definitions of Adverse Events

Adverse Event

An adverse event (also known as an adverse experience) is defined as any untoward medical occurrence associated with the use of a medical device in humans, whether or not considered device related. More specifically, an adverse event (can be any unfavorable and unintended sign (e.g., an abnormal laboratory finding), symptom, or disease temporally associated with the use of a device, without any judgment about causality. An adverse event can arise from any use of the device (e.g., off-label use, use in combination with another treatment or drug).

Adverse reaction

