Kaplan Meier survival analyses will be used to analyze the following secondary endpoints: 1) progression-free survival at 6 months and 2 years, 2) median time-to-death and overall survival at 2 years and 3) duration of TTF use. Log rank tests may be used in Kaplan Meier analyses to test for differences in survival curves amongst known prognostic factors such as age, duration and compliance of TTF use, KPS, extent of resection, IDH mutation status, and MGMT methylation status. The objective response by modified RANO criteria will be summarized with counts and percentages following trimodal treatment and at 2 years. The rate of TTFields compliance will be reported as the percentage of patients who used TTFields at least 75% of the minimum recommended usage of 18 hours a day on average, as assessed monthly.

The intention-to-treat analyses may be supplemented by per-protocol analyses, if the percentage of patients who did not follow standard of care recommendations as outlined for adjuvant and maintenance therapy following trimodal treatment is high.

Power Calculation

As we are expecting that patients will be more susceptible to skin irritation with concurrent therapy than with successive therapy, we focus on severe skin irritation as our endpoint for this power calculation. We expect 5% of patients will experience severe skin irritation based on a 2% rate in the Stupp et al. 2015 study (EF-14)²⁴ which used TTField therapy following initial chemoradiation treatment. Assuming a sample size of 30 patients of whom 5% experience severe skin irritation, we can say with 95% confidence that the true percentage of patients with severe skin irritation is no lower than 2% and no higher than 21% based on a one-sample binomial proportion. Outside of severe skin toxicity, the rate of any adverse event is not expected to differ significantly from that established by the EF-14 trial.

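### Log-rank tests of PFS and OS grouped by duration of TTFields use are biased toward longer use; drop duration as a grouping factor

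*Combined protocol and SAP*

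**What the plan says.** Section 8 (Statistical Considerations) permits, but does not require, log-rank tests for "differences in survival curves amongst known prognostic factors such as age, duration and compliance of TTF use, KPS, extent of resection", followed by IDH and MGMT status. The same paragraph makes duration an outcome, to be analysed by Kaplan-Meier: "median time-to-death and overall survival at 2 years and 3) duration of TTF use". Section 6, Secondary Study Endpoints, also lists it: "Median duration of TTFields use and rate of TTF compliance".

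Three places tie the end of device use to the survival events:

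- Section 6, Treatment Modalities, Optune item 3: "Treatment will be continued until tumor progression, death, or unacceptable side effects to patient".
- Section 7a: "Subjects will continue to receive study treatment until confirmed tumor progression, unacceptable toxicity, or other discontinuation criteria as described".
- Section 7b, Evaluation of Pseudoprogression: "If that follow-up scan confirms progression, the patient shall be taken off the study treatments".

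Use can also end for other reasons, such as patient request, toxicity, poor compliance or intercurrent illness (Section 6, Criteria for Removal from Study Therapy). It is capped at 24 months. The plan states no cut-point for duration, no significance level for these tests, and no landmark or time-dependent method.

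**The concern.** Duration is treated as a baseline covariate, but the outcome limits it. A patient who progresses at month 3 normally cannot have six months of use; one who is progression-free at month 12 can. Grouping by total duration therefore sorts patients partly by the event being tested, and the long-use group carries guaranteed event-free time. This is immortal-time bias, and it runs toward longer use.

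Section 6 wants the secondary endpoints to supply trends for later efficacy trials, and the secondary hypothesis in the synopsis is that early, continued use prolongs progression-free and overall survival. The bias points the same way. A spurious finding that longer use goes with longer survival could be read as dose-response and carried into the design of the next trial.

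**Working it through.** The documents give no figure for these tests, so there is nothing to reproduce. The check is a simulation in which use has no effect on progression or death.

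**Inputs from the documents**

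- n = 30 (Section 1); cap of 24 months (Section 6).
- Median PFS 7.1 months, from Section 3d. That trial tested the device "in combination with temozolomide maintenance after surgery and chemoradiation versus temozolomide alone", so its clock starts later than Day 1 here.
- The schedule reads "Adjuvant TMZ therapy, Day 1 of Cycle 1 (Study Day 78", so the clock can be shifted by 78 − 1 = 77 days: 7.1 + 77/30.44 = 9.6 months. Both values are used.

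**Inputs assumed**

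- Exponential times; median post-progression survival 6, 10 or 15 months.
- Unrelated stopping never, or at a median of 3, 6, 12, 18 or 30 months.
- Split at median duration; two-sided 5% test.

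**Model**

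- Death = progression time + post-progression time.
- Duration = min(progression, unrelated stop, 24 months).
- Count the trials with z beyond 1.96 in favour of longer use. There are 20,000 trials per setting, so the Monte Carlo standard error is at most 0.4 points.

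**False results favouring longer use.** Each OS cell lists post-progression medians of 6/10/15 months.

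| Unrelated stop, median | PFS (7.1) | OS (7.1) | PFS (9.6) | OS (9.6) |
|---|---|---|---|---|
| never | 100% | 89/69/50% | 100% | 97/85/68% |
| 30 months | 96-97% | 72/50/35% | 95% | 78/61/45% |
| 18 months | 89-90% | 59/41/29% | 85% | 64/47/35% |
| 12 months | 78% | 47/32/23% | 70% | 50/36/27% |
| 6 months | 50-51% | 28/19/14% | 40% | 27/19/15% |
| 3 months | 25% | 14/10/9% | 18-19% | 13/10/8% |

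A baseline grouping factor gives 5-6% two-sided, about 3% in one direction.

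**Other cut-point.** With a fixed 6-month cut and unrelated stopping, the ranges are 11-97% for PFS and 3-76% for OS. OS can therefore be near nominal when unrelated stopping is very early.

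**Second parametrisation.** A separate simulation (2,000 trials per setting) took the PFS/OS medians 7.1/20.5 months from Section 3d and set median post-progression survival to 20.5 − 7.1 = 13.4 months. With unrelated stopping never, or at a median of 24, 12, 6 or 3 months, it gave 100, 94, 80, 51 and 25% for PFS, and 56, 36, 27, 15 and 10% for OS. Over a wider set (PFS medians 4.0-10, OS inputs 15.6-24.5 months), results favouring shorter use were at most 0.3% for PFS and 0.9% for OS. The bias runs one way.

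**Compliance.** This is average daily use, so it is not immortal time. With assumed hours of mean 16 and SD 3, split at 0.75 × 18 = 13.5 hours a day, two-sided error is 7-8% for PFS and 6-7% for OS if hours are unrelated to disease course. If hours fall by 4 a day in the last month before progression (assumed), it is 21-29% and 10-17%. If they fall by 8 a day over the last two months (assumed), it is 59-73% and 19-48%. The documents make such a fall plausible but do not show it.

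**The case against.** - **The tests are optional and unpowered.** Section 8 says they may be used, Section 6 disclaims power, and the synopsis says the secondary hypothesis needs validation in a larger trial. This stands and limits the severity. It does not remove the bias: low power does not protect a test that rejects often under the null.
- **The top of the OS range does not match the cited survival.** A 6-month post-progression median implies a median OS of 15.8 months (PFS 7.1) or 18.7 months (PFS 9.6). The device arm in Section 3d had 20.5, or about 20.5 + 2.5 = 23.0 on the shifted clock. A 10-month value fits better (20.6 and 23.7). OS error is then 10-50% or 10-61% with unrelated stopping, and 69% or 85% without. This stands. Four of the five settings above 50%, out of 30 with unrelated stopping, use the 6-month value.
- **The 100% PFS case is degenerate.** If only progression or the cap ends use, duration is essentially time to progression. The protocol lists other reasons to stop, so this is a limiting case. The documents give neither a stopping rate nor a cut-point, so the direction is certain and the size is not.
- **Use is known to predict survival.** Section 3d reports that compliance predicted survival in a registry of recurrent disease. That concerns hours per day, not duration, and does not make duration a baseline factor.

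**Conclusion.** The concern holds. As written, a log-rank test by duration of use favours longer use under no effect. For PFS a false result is more likely than not unless unrelated stopping is early: 70-97% at a stopping median of 12 months or more, 40-51% at 6 months and 18-25% at 3 months. For OS the error is usually well above nominal but mostly below one half. These sizes rest on exponential times, a median split and assumed rates of unrelated stopping; the direction follows from the protocol's own rules for ending use. The consequence is confined to interpretation of an optional secondary analysis. The primary safety endpoints, stopping rules and sample size are unaffected. Compliance shares the post-baseline problem in weaker form, because it is assessed monthly with no fixed window.

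**What to change.** In Section 8, delete duration of TTFields use from the log-rank factors and report it by Kaplan-Meier only, as the same paragraph already plans. Keep age, KPS, extent of resection, IDH and MGMT. This costs nothing.

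For compliance, either remove it from tests that start at time zero, or test it only over a fixed early window with a landmark. One optional version, exploratory and non-causal, takes patients alive and progression-free at Day 106, groups them at the median of mean daily hours from Day 1 to Day 106, and starts the clock there. State in advance:

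- how patients on an officially reduced schedule are grouped (for example, as a separate category), since Section 6 exempts them from the non-compliance rule;
- how an unconfirmed suspicious scan counts, since the Day 106 assessment uses the Cycle 1 Day 1 MRI. The confirmatory scan that Section 7b recommends about 4 weeks later would fall near Day 78 + 28 = 106.

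The landmark has a price. Day 106 is 105/30.44 = 3.45 months after Day 1, so the expected loss is 1 − 0.5^(3.45/7.1) = 29% or 1 − 0.5^(3.45/9.6) = 22%, about 7-9 of 30 patients. It says nothing about later use. Its two-sided error is 5-7% if hours are unrelated to disease course, and up to 10% for PFS and 7% for OS if hours fall by 8 a day in the two months before progression (assumed). A 13.5-hour cut does worse, at up to 18% and 11%. It also needs usage data from Day 1. Monthly extraction and the study calendar suggest these exist, but the trimodal-phase visit lists name no compliance assessment, so availability must be confirmed.

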Study Hypothesis:	TTFields has been shown to be safe and efficacious in large trials with glioblastoma patients in combination with adjuvant temozolomide but concurrent use together with trimodal therapy has not been examined in clinical trials. Our primary hypothesis is that the TTFields treatment, if initiated concurrently along with radiation and temozolomide therapy, would not significantly alter the safety profile. Secondarily, continuation of early initiated TTF along with adjuvant temozolomide treatment as per the standard of care would increase progression and overall survival. The primary hypothesis is safety and will be tested directly in this trial, but the secondary hypothesis would be assessed only with preliminary observations and need validation in a larger trial that is statistically powered for that investigation.
Sample Size:	30 patients total, 6 included in the first safety lead-in and 15 in the second safety lead-in.
Study Population:	Patients with newly diagnosed histologically confirmed glioblastoma after maximally safe resection, with MGMT methylation status in process, are eligible for enrollment.
Primary Endpoint:	The primary endpoint is safety and tolerability of the combined use of TTFields added to standard chemoradiation and TMZ.
Secondary Endpoints:	Our secondary endpoints will be progression-free and overall survival, imaging response by RANO criteria, and duration and compliance of TTF use.

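### The 95% limits of 2% and 21% in the Power Calculation do not follow from the stated 5% of 30 patients, and the interval method is not named

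*Combined protocol and SAP*

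**What the plan says.** The Power Calculation, at the end of Section 8, takes severe skin irritation as its endpoint. It sets the anticipated rate by reference to EF-14: "We expect 5% of patients will experience severe skin irritation based on a 2% rate". It then fixes the inputs: "Assuming a sample size of 30 patients of whom 5% experience severe skin irritation". From these it states, with 95% confidence, that "the true percentage of patients with severe skin irritation is no lower than 2% and no higher than 21" (percent). The only indication of method is that the result is "no higher than 21% based on a one-sample binomial proportion". The section gives no event count, does not say that a count was rounded, and names no interval method. The synopsis agrees on the sample size: "30 patients total, 6 included in the first safety lead-in and 15 in the second safety lead-in".

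**The concern.** The sentence supplies the sample size, the rate and the confidence level, so a reader should be able to recompute the limits. At the stated rate that cannot be done. To recover 2% and 21% the reader has to guess a different rate and choose an interval method.

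This is the plan's only stated precision for its 30 patients. The rest of Section 8 treats 30 as a requirement and provides for extra recruitment to reach it, so this is where an IRB member, a DSMC statistician or the designer of the later phase II trial would look to see what 30 patients can show about the toxicity that the protocol singles out.

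**Working it through.** **Inputs**, all from the Power Calculation in Section 8: n = 30, rate p = 5%, confidence 95%. Both a lower and an upper limit are given, so the interval is read as two-sided, with z = 1.960 and z² = 3.8415. A match means that both limits round to 2% and 21%, the precision the plan reports.

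**Implied count.** 0.05 × 30 = 1.5 patients.

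**Wilson formula.** Centre = (p + z²/2n) / (1 + z²/n). Half-width = z × √[p(1−p)/n + z²/4n²] / (1 + z²/n). With n = 30: z²/2n = 0.06402, z²/4n² = 0.001067 and 1 + z²/n = 1.12805.

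**At the stated 5%.**
- Centre = (0.05 + 0.06402) / 1.12805 = 0.1011
- Half-width = 1.960 × √(0.001583 + 0.001067) / 1.12805 = 0.0894
- Limits: **1.16% to 19.05%**, not 2% and 21%

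**At 2 of 30 (6.67%).**
- Centre = (0.06667 + 0.06402) / 1.12805 = 0.1159
- Half-width = 1.960 × √(0.002074 + 0.001067) / 1.12805 = 0.0974
- Limits: **1.85% to 21.32%**, which round to the plan's 2% and 21%

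**Other methods**, two-sided 95%, n = 30:

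| Method | At 5% (1.5/30) | At 2/30 (6.7%) |
|---|---|---|
| Wilson | 1.16–19.05 | **1.85–21.32** |
| Wilson, continuity-corrected | 0.59–21.32 | 1.16–23.51 |
| Exact (Clopper-Pearson, beta form) | 0.36–19.71 | 0.82–22.07 |
| Jeffreys | 0.82–17.22 | 1.41–19.71 |
| Uniform-prior Bayes | 1.36–19.12 | **2.04–21.42** |
| Logit | 1.01–21.37 | 1.67–23.07 |
| Agresti-Coull | −0.05–20.26 | 0.80–22.37 |
| Wald | −2.80–12.80 | −2.26–15.59 |

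Four further methods at 5% also fail: log (1.05–23.79), log(−log p) (0.65–16.87), log(−log(1−p)) (1.03–22.44) and arcsine (0.22–15.48). Across all twelve, the highest lower limit at 5% is 1.36%, so none rounds to 2%. Other confidence levels (90%, 97.5% and 99%) were tried with most of these methods and gave no match at 5% either.

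**Working backwards.** The rates at which both limits round to 2% and 21% are about 6.05% to 6.80% for Wilson, 5.99% to 6.72% for the uniform prior, 7.22% to 7.92% for Jeffreys, 7.65% to 8.40% for log(−log p) and 8.83% to 8.92% for arcsine. The other seven methods have no solution between 1% and 12%. The only multiple of 1/30 in any of these ranges is 2/30 = 6.67%, in the Wilson and uniform-prior ranges. By Wilson, one event gives 0.59% to 16.67% and three give 3.46% to 25.62%, so neither fits.

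**The case against.** The strongest counter-argument is that only the failure to reproduce is proven. The text says 5% twice and gives no count. At 5%, the continuity-corrected Wilson and logit intervals both give an upper limit of 21%, so the upper limit could be right for 5% and only the lower one wrong, by about one point. Wilson is also not the only method that fits 2 of 30. A planning calculation need not use a whole count. And nothing in the trial depends on this interval: the stopping rules count DLTs (2 of 6, 5 of 15, more than 33%), and Section 8 plans to report the primary endpoints as counts and percentages.

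Much of this stands. The rounding of 1.5 to 2 is an inference, the method cannot be identified with certainty, and a rate of 5% may be used for planning. The missing method name alone would only be missing detail. What does not give way is the mismatch: no method tried yields both limits at 5%, and rounding the result cannot turn 1.16% into 2% or 19.05% into 21%.

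**Conclusion.** The concern holds, as a minor error in a stated figure. Confidence is high that the pair 2% and 21% does not correspond to 5% of 30. That 2 of 30 was used is the best explanation, but it is not established.

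The size and direction of the discrepancy depend on the comparison:
- Against Wilson at 5%, the lower limit is about 0.8 points high (2% versus 1.2%) and the upper about 2 points high (21% versus 19.1%).
- Against continuity-corrected Wilson or logit at 5%, only the lower limit is off (0.6% or 1.0%).
- Against the exact interval at 2 of 30, the upper limit is about 1 point low (21% versus 22.1%).

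The conclusion assumes a two-sided 95% interval and agreement judged to the whole percent. N = 30 is a premise of the sentence and not its result, so neither the sample size nor the DLT stopping rules change.

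**What to change.** Replace the sentence with one that names the rate or count and the method. Either of these can be reproduced:

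- *If 2 of 30 patients (6.7%) have severe skin irritation, the 95% Wilson score interval is 1.8% to 21.3%.*
- *At a rate of 5% with n = 30, the 95% Wilson score limits are 1.2% and 19.1%.*

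If a range of outcomes would help, the Wilson intervals for neighbouring counts are 0% to 11.4% (0 of 30), 0.6% to 16.7% (1 of 30) and 3.5% to 25.6% (3 of 30). These are optional.

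The cost is one sentence. Sample size, stopping rules, endpoints and data collection stay as they are.
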